### CLARIFICATIONS FOR AN INTERVIEWER:

What does the test show: it's a test for antibodies. It shows if you have had a coronavirus infection earlier (as this infection is often asymptomatic or similar to other diseases). It does not show if you are currently infected. It is free of charge.

Results of the test will not be reported to state organizations.

What are Scandinavia clinics: it's the largest private clinics chain in St. Petersburg, one of the centers of urgent medical care in case of coronavirus infection.

Q1001 Single choice from 'Q1001 list'

We guarantee that your answers will be kept confidential. For the quality control of my work, this call will be recorded, and the record will be deleted after the end of the study. Do you agree to proceed to a survey?

How can I refer to you?

informationText('Respondent name: ' + Q.openValueTxt);

Q1

Sex

(DON'T READ THE QUESTION, REGISTER THE ANSWER BASED ON EARLIER ANSWERS)

Single choice from 'Q1 list'

1 Male

2 Female

Q2

Please tell me, do you live in St. Petersburg?

(DON'T READ ANSWERS)

(A SINGLE ANSWER) Single choice from 'Q2 list'

1 Yes

2 No

If Q2=2, terminate the interview

Q3 Single choice from 'Q3 list'

In which district of St. Petersburg do you live?

(DON'T READ ANSWERS)

(A SINGLE ANSWER)

1 admiraltEiskiy

2 vasileostrOvskiy

3	vYborgskiy	
4	kAlininskiy	
5	kIrovskiy	
6	kOlpskiy	
7	krasnogvardEiskiy	
8	Krasnoselskiy	
9	KronshtAdtskiy (KronshtAdt)	
10	Kurortniy	
11	Lomonosovskiy	
12	Moskovskiy	
13	Nevskiy	
14	PetrogrAdskiy	
15	PetrodvortsOviy	
16	primOrskiy	
17	pUshkinskiy	
18	frUnzenskiy	
19	Centralniy	
998	OTHER (explain)	OpenValueTxt

Q4     Numeric

How old are you in full years?

If Q4(ValueInt<18), terminate the interview

Q5     Single choice from 'Q5 list'

Please tell me if since the beginning of February, you have been to somewhere outside of St. Petersburg and Leningrad region?

(DON'T READ ANSWERS)

(A SINGLE ANSWER)

1       Yes

2       No

Q6     Single choice from 'Q6 list'

Q5=1

Have you traveled abroad since the beginning of February?

1       Yes

2       No

Q7     Single choice from 'Q7 list'

Among the people who you have met after the 1st of March, are there people who have traveled abroad in February or later?

(DON'T READ ANSWERS)

(A SINGLE ANSWER)

1       Yes

2       No

999            (DON'T READ) Not sure

Q8

Have you exited your home during the last week (7 days)?

(DON'T READ ANSWERS)

(A SINGLE ANSWER) DisableReordering Single choice from 'Q8 list'

1       Yes

2       No

Q9     Single choice from 'Q9 list'

Q8=1

How often have you been outdoors during the last week (7 days)?

(A SINGLE ANSWER)

Q10 Single choice from 'Q10 list'

Q8=1

How much time have you spent out of your home when you went out most recently?

(IF THE ANSWER CONTAINS INTERVAL, REGISTER THE UPPER BORDER.

REGISTER HOURS OR MINUTES — 30 min, 20 min

IF THE ANSWER CONTAINS HOURS AND MINUTES, REGISTER AS IT IS: 1 h 10 min, 2 h 40 min)

999 (DON'T READ) Not sure

Q11 Multiple choice from 'Q11 list'

Q8=1

Which of the following places have you visited during the last week?

(ANY NUMBER OF ANSWERS)

1 Work

2 Metro and other public transport, including taxi

3 A pharmacy

4 A shop or a market

5 A post office, a bank, an ATM, a medical institution

6 I have not been to any of these places

Q12

Have you had any examination for coronavirus?

(DON'T READ ANSWERS)

(A SINGLE ANSWER) DisableReordering,

Blocking

Single choice from 'Q12 list'

1 Yes

2 No

Q121 Single choice from 'Q121 list'

Q12=1

The result of this examination was:

(A SINGLE ANSWER)

1 Positive

2 Negative

3 I don't know

999 (DON'T READ ANSWERS) Not sure

Q13 Single choice from 'Q13 list'

Do you or do you not follow information regarding coronavirus? If you follow, do you do it continuously or once in a while?

(DON'T READ ANSWERS)

(A SINGLE ANSWER)

1 Follow continuously

2 Follow once in a while

999 (DON'T READ ANSWERS) Not sure DisableReordering

Q15 Single choice from 'Q15 list'

Q8=1

Were you wearing a mask when leaving your home during the last week?

(DON'T READ ANSWERS)

(A SINGLE ANSWER)

1 Yes

2 No

Q16 Single choice from 'Q16 list'

Q8=1 and Q15=1

Were you wearing a mask while just outdoors?

(DON'T READ ANSWERS)

(A SINGLE ANSWER)

1 Yes

2 No

Q17

Can you say that now you wash your hands more often than before the epidemics?

(DON'T READ ANSWERS)

(A SINGLE ANSWER) Single choice from 'Q17 list'

1 Yes

2 No

999 (DON'T READ) Not sure

Q19

In your opinion, should the limitations for public have been stricter or not?

(DON'T READ ANSWERS)

(A SINGLE ANSWER) DisableReordering Single choice from 'Q19 list'

1 Yes, they should have been

2 No, they should not have been

999 (DON'T READ) Not sure DisableReordering

Q20 Single choice from 'Q20 list'

Q19=2

In your opinion, should the limitations for public have been less strict or not?

(DON'T READ ANSWERS)

(A SINGLE ANSWER)

1 Yes

2 No

999 (DON'T READ) Not sure

Q21

How would you evaluate your health?

(A SINGLE ANSWER) DisableReordering Single choice from 'Q21 list'

1 Very good

2 Good

3 Satisfactory

4 Bad

5 Very bad

Q22 Single choice from 'Q22 list'

Please remember how many times you have been ill since February. Answer about your own feelings, not only when you took a sick leave.

(IF THE ANSWER CONTAINS AN INTERVAL, REGISTER THE UPPER BORDER)

999 (DON'T READ) Not sure

Q23 Single choice from 'Q23 list'

Do you seek out preventative examinations in state or private clinics?

(DON'T READ ANSWERS)

(A SINGLE ANSWER)

1 Yes

2 No

999 (DON'T READ) Not sure DisableReordering

Q24 Single choice from 'Q24 list 1'

Do you live alone or with others?

(DON'T READ ANSWERS)

(A SINGLE ANSWER)

- 1 I live alone
- 2 I live with other people

Q241 Numeric

Q24=2

How many people live in your household (except you)?

Q242 Multiple choice from 'Q242 list'

Q24=2

Are there following categories among the people who live with you (except you)?

(ANY NUMBER OF ANSWERS)

(READ ANSWERS WITH PAUSES)

- 1 Minors (younger than 18 years)
- 2 Elderly (older than 65 years)
- 3 Your husband/wife, permanent partner
- 4 (DON'T READ; REGISTER IF NO OTHER ANSWER HAS BEEN SELECTED) Nothing applies

Q25 Single choice from 'Q25 list'

How would you define your income level before the start of pandemic?

(A SINGLE ANSWER)

- 1 It was very hard. We did not have enough money even for food
- 2 We had money for food, but buying clothes was a problem
- 3 We had money for food and clothes but buying a fridge, a TV set, furniture would be a problem
- 4 We could easily buy a fridge, a TV set, furniture, but did not have enough money for something bigger
- 5 We can easily buy a car, but we don't have enough money for bigger things, like a flat or a summer house
- 6 We can afford almost everything: a car, a flat, a summer house and many other things

Q26 Single choice from 'Q26 list (Yes No ДРУГОЕ)'

Tell me please if you were working at the moment of the February 1st.

(DON'T READ ANSWERS)

(A SINGLE ANSWER)

IF A PERSON IS ON MATERNITY LEAVE, REGISTER AS UNEMPLOYED

998 Other (clarify)OpenValueTxt,  
DisableReordering

Q27 Single choice from 'Q26 list (Yes No ДРУГОЕ)'

Were you studying at the moment of the February 1st?

(DON'T READ ANSWERS)

(A SINGLE ANSWER)

IF A PERSON CONSIDERS SOMETHING AS STUDYING, REGISTER ACCORDING TO THEIR WORDS

(DO NOT GUIDE TO ANSWER; ASK TO ANSWER ACCORDING TO THEIR OWN OPINION ABOUT IF IT IS OR IT IS NOT STUDYING)

998 Other (clarify)OpenValueTxt,  
DisableReordering

Q28 Single choice from 'Q26 list (Yes No ДРУГОЕ)'

At the moment of the February 1st, were you receiving a pension, a welfare, a stipend from the state?

(DON'T READ ANSWERS)

(A SINGLE ANSWER)

998 Other (clarify)OpenValueTxt,  
DisableReordering

Q29 Single choice from 'Q26 list (Yes No ДРУГОЕ)'

Q26=2 or Q26=998

Were you looking for a job during the last 12 months?

(DON'T READ ANSWERS)

(A SINGLE ANSWER)

The question implies the last 12 months until now.

998 Other (clarify)OpenValueTxt,  
DisableReordering

Q30 Single choice from 'Q26 list (Yes No ДРУГОЕ)'

Q26=1

You said that you worked at the moment of the February 1st.

At that moment, were you managing others or no?

(DON'T READ ANSWERS)

(A SINGLE ANSWER)

998 Other (clarify)OpenValueTxt,  
DisableReordering

Q31 Single choice from 'Q26 list (Yes No ДРУГОЕ)'

Q26=1 and Q27=2 and Q30=2

Did your job at that moment involve physical work?

(DON'T READ ANSWERS)

(A SINGLE ANSWER)

998 Other (clarify)OpenValueTxt,  
DisableReordering

Q32 Single choice from 'Q32 list'

Q26=1

Currently, do you work as usual, or is your timetable/working organization different from those before the epidemics (remote work, coerced days off etc.)?

(DON'T READ ANSWERS)

998 OpenValueTxt,  
DisableReordering

Q321 Single choice from 'Q321 list'

Q32=2

Which of the following situations is most similar to your timetable/working organization during the epidemics?

(A SINGLE ANSWER)

1 I work remotely

2 I am on paid leave

3 I've lost my job or on unpaid leave, I spend my savings or use help from friends and family.

4 I've lost my job or on unpaid leave, I have to do some casual jobs

Q33 Single choice from 'Q33 list'

What is your education level?

(DON'T READ ANSWERS)

(A SINGLE ANSWER)

- 1 Initial/ unfinished secondary education
- 2 Complete secondary education
- 3 Special secondary, technical secondary, initial professional education
- 4 University education

Q34

Do you have the Russian Federation nationality?

(DON'T READ ANSWERS)

(A SINGLE ANSWER) Single choice from 'Q34 list'

- 1 Yes
- 2 No

Q35 Numeric

Since what year have you been living in St. Petersburg?

Q36 Multiple choice from 'Q36 list'

let code = Q8001.getCheckedCode(); let texts = {

1: 'Thank you for your answers. You are offered free testing for anti-coronavirus antibodies

2: 'Thank you for your answers. You are offered free testing for anti-coronavirus antibodies

3: 'Thank you for your answers. You are offered free testing for anti-coronavirus antibodies 4: 'Thank you for your answers. You are offered free testing for anti-coronavirus antibodies

};

Q.text = code in texts ? texts[code] : 'Code text not found' + code;

Thank you for your answers!

You are offered free testing for anti-coronavirus antibodies at a Scandinavia clinic; it will show if you have or have not had the infection (or have it now). This is needed to evaluate the prevalence of this infection in our city, even if some people have had in in asymptomatic form.

a) If you agree, give me please your contact phone number, first and patronymic names (no last name). In the next 5 days, clinic representatives will contact you to discuss a moment for testing which suits you. Do you agree?

b) If you agree, give me please your contact phone number, first and patronymic names (no last name). In the next 5 days, clinic representatives will contact you to discuss a moment for testing which suits you and to explain how you can call for a free taxi to go to the clinic as a participant of this study. Do you agree?

CLARIFICATIONS FOR AN INTERVIEWER:

Any questions related to the testing results waiting time, its medical characteristics etc. might be asked to a clinic representative when they contact the respondent.

- 1 Name and patronymic name: OpenValueTxt
- 2 Contact phone number: OpenValueNum
- 3 No, do not agree Blocking

# Appendix 2

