## List of Appendices

**Appendix 1. Questionnaire for telephonic survey.**

**Appendix 2. Medical questionnaire.**

**Appendix 3. SARS-CoV-2 antibody test results.**

**Appendix 4. Participant Information Sheet and Informed Consent Form.**

## **1. Introduction**

Population analysis of infection spreading is one of the key methods of new epidemics control. The World Health Organization has included population serological surveys, which help to visualize the new virus distribution, into a list of essential assessments during the current epidemics, along with the vaccine development and search for effective treatments for severe disease. Such studies help understand real disease spread and a real proportion of fatal outcomes among the patients with a disease and infected persons. Initial studies have shown the presence of immune response to an earlier SARS-CoV-2 infection.

Regarding the SARS-CoV-2 pandemic, the population assessment of immune response is recommended until the year 2024, as currently there is a discussion of a high risk of second and further peaks of new coronavirus epidemics. Initial studies performed in the state of New York have shown that up to 14% state residents and 21.2% of New York City residents had had the infection and had developed antibodies. In the states of Idaho and California, there were not more than 2% of such people.

To evaluate the proportion of people who have had the disease in a whole population (a city, a region, a country), the representativeness of a sample needs a strict approach. The methodology of a serological study is in many aspects similar to a sociological survey but is more complicated due to the use of serological test results. In addition, the population characteristics of these tests, i.e. sensitivity and specificity, are not always well-known. A serological study sample should be representative for the general population (age groups, gender, place of living, mobility during the epidemics).

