## 2.2.Secondary objectives

- To evaluate the incidence in the cohort study.
- To evaluate the relation between the risk of infection and several factors (mobility, social characteristics).
- To evaluate individual immune dynamics (seroconversion, seroreversion).
- To compare the proportion of participants with positive test results between age (<20, 20-29, 30-39, 40-49, 50-59, 60-69, >70) and gender groups.

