### 5.3.2. Secondary objectives

#### Cross-sectional study:

- To evaluate the relation between different sociodemographic factors and presence of infection by means of calculation of the adjusted prevalence ratios in different groups.

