**8. Have you used public transport in the last 2 weeks? If yes, how often?**

- ☐ At least once a day per week ☐ Several times per week
- ☐ Once a week or less ☐ Never

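### Everyday mobility and mask use are asked only for the last outing, 7 days or 2 weeks, but the cross-sectional outcome is any earlier infection, so those associations largely relate past infection to later behaviour

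*Protocol*

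**What the plan says.** Protocol section 2.2 lists as a secondary objective "To evaluate the relation between the risk of infection and several factors (mobility, social characteristics", with mobility named first and no time window. The Introduction, describing what a representative serological sample should reflect, lists "age groups, gender, place of living, mobility during the epidemics".

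The outcome is past infection. The interviewer notes in Appendix 1 say of the test: "It shows if you have had a coronavirus infection earlier (as this infection is often asymptomatic or similar to other diseases". They add that it does not show current infection.

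The everyday behaviour items look back only a short way:
- Appendix 1, Q8: "Have you exited your home during the last week (7 days". Q9 (frequency outdoors) has the same window.
- Q10 asks about the most recent outing only.
- Q11: "Which of the following places have you visited during the last week". Q15 (mask on leaving home) also covers the last week, and Q16 follows from Q15.
- Appendix 2, item 8: "Have you used public transport in the last 2 weeks".

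Other items reach further back. Q5 and Q6 cover travel outside the region and abroad since the beginning of February. Q7 covers contact with travellers after 1 March. Appendix 2 item 5 covers hospital or clinic visits since February. Q26 fixes employment at a date ("Tell me please if you were working at the moment of the February 1st"), and Q32 and Q321 record how work has changed, including remote work.

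On analysis, section 5.3 lists regression coefficients of test results on observed characteristics. Section 5.3.2 plans, for the cross-sectional part, to relate sociodemographic factors to "presence of infection by means of calculation of the adjusted prevalence ratios in different groups". For the cohort it plans rate ratios and leaves participants positive at the first test out of the incidence analysis.

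**The concern.** A risk factor has to be measured for the period in which infection could have occurred. Here the everyday items describe the days just before the interview, while the infection may lie weeks or months back. Section 3.2.2.3 excludes people with acute respiratory symptoms at survey or test, which makes an infection inside the recall window less likely still among those tested.

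Current behaviour is also a doubtful stand-in for earlier behaviour. The questionnaire itself presupposes change: it refers to self-isolation, to restrictions on the public, and to remote work or enforced days off. Some respondents have been ill since February (Q22) or already know a coronavirus test result (Q121), and may go out less because of it.

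Two things are at stake. Misclassification pulls a real association towards no effect and costs power. Behaviour that changed because of infection can push it further, in principle past no effect. Covariate adjustment repairs neither. Because the windows are fixed in the questionnaire, no later analysis plan can recover March-April commuting that was never asked about.

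**Working it through.** The protocol gives no figure for this objective. The one planning value used below is its 10% prevalence (section 5.1), where the sample-size statement checks: 1.96² × 0.1 × 0.9 / 0.02² − 4 = 860.4, which is below 900 as stated.

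**Step 1, window against period.** The protocol sets no start for the infection period, so 1 February 2020 is an assumption taken from the questionnaire's own reference dates. The Appendix 2 form is dated May/June 2020. From 1 February to 1 May is 90 days, and to 30 June 150 days.
- 7-day window: 7/90 = 7.8% to 7/150 = 4.7% of the period.
- 14-day window: 14/90 = 15.6% to 14/150 = 9.3%.

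These shares show how little of the period is observed. They do not measure bias.

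**Step 2, dilution.** Assumptions: prevalence P = 0.10, share mobile early e = 0.40, true prevalence ratio R = 2.0, and current mobility agreeing with earlier mobility with probability a, the same for infected and non-infected.
- Prevalence in the early non-mobile: r0 = P / (eR + 1 − e) = 0.10/1.40 = 0.0714. In the early mobile: r1 = 0.1429.
- Share recorded as mobile: q1 = ea + (1 − e)(1 − a).
- Prevalence in those recorded as mobile: c1 = [ea·r1 + (1 − e)(1 − a)·r0] / q1. In the rest: c0 = (P − q1·c1) / (1 − q1).

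| a | q1 | c1 | c0 | observed ratio |
|---|---|---|---|---|
| 0.8 | 0.44 | 0.1234 | 0.0816 | 1.51 |
| 0.7 | 0.46 | 0.1149 | 0.0873 | 1.32 |
| 0.6 | 0.48 | 0.1071 | 0.0934 | 1.15 |

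With half the sample mobile instead of 40%, the ratios are nearly the same: 1.50, 1.31 and 1.14. An unadjusted comparison of 500 with 500 participants then has power of 56%, 29% and 10%, against 94% without misclassification.

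**Step 3, what reversal needs.** Take a = 0.7. The share currently mobile among the infected is (0.0571 × 0.7 + 0.0429 × 0.3)/0.10 = 52.9%. Among the non-infected it is (0.3429 × 0.7 + 0.5571 × 0.3)/0.90 = 45.2%. The observed ratio reaches 1.0 when the infected share falls to 45.2%, an average relative drop of 1 − 45.2/52.9, or about 14%, across all infected people. At a = 0.8 the drop needed is about 21%.

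Now suppose each infected person who changes behaviour becomes about 29% less likely to be mobile (0.50 instead of 0.70 among the formerly mobile, 0.214 instead of 0.30 among the others). Still at a = 0.7:
- 30% of the infected change: ratio 1.12.
- 50% change: ratio 1.00.
- All change: ratio 0.76.

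**The case against.** The strongest reply has four parts.

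First, a reader might infer that the protocol asks about mobility as a whole only for recent days. It does not. Q5 and Q6 stand shortly before Q8 and ask about travel since February. Q7 and the clinic-visit item also look back, and Q26 with Q32 and Q321 shows who worked in February and now works from home. This stands, and it confines the point to everyday local movement and masks. Those longer items do not measure commuting by public transport, shopping or attendance at work in March-April.

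Second, the sentence on prevalence ratios in section 5.3.2 speaks of sociodemographic factors and does not name mobility. Which covariates enter which model may properly sit in an analysis plan that is not shown. The recent items may also serve to model the decision to attend for testing (section 5.2). This stands too: the protocol does not fix a prevalence ratio on last-week mobility. But section 2.2 promises the mobility relation, section 5.3 regresses test results on observed characteristics, and the short windows bind whichever model is chosen.

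Third, the cohort part already gives the right time order. Participants positive at the first test are left out of incidence, and section 3.1 has follow-up questionnaires covering the time since that test. This stands, apart from infections too recent for the test to detect at the visit.

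Fourth, a reader might infer that the sign of the association will reverse. Appendix 1 itself calls the infection often asymptomatic, so many infected people would have no reason to change. The ratio of 0.76 needs every infected person to cut back and is a worst case.

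**Conclusion.** The point holds for the cross-sectional associations of test result with the recent mobility and mask items (Q8-Q11, Q15-Q16, Appendix 2 item 8). They largely describe behaviour after infection and should not be read as risk estimates.

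The likely consequence is dilution: a true ratio of 2.0 appears as 1.51 to 1.15 when agreement between current and earlier mobility is 80% to 60%. That range rests on 10% prevalence, 40% mobile early and equal misclassification in infected and non-infected people. Of these, only the prevalence comes from the protocol. No agreement rate is given in the protocol, so the true size is unknown. Reversal is possible but needs a large share of infected people to have reduced their mobility, about half of them in the scenario worked above.

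The documents do not support the reading that the whole mobility objective fails, since the cohort rate ratios are largely free of the fault. Nor is the primary prevalence estimate affected. This is a weakness in one named secondary objective, worth correcting because the questionnaire fixes it and the remedy is cheap.

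**What to change.** (a) Add one or two recall items to Appendix 1 on going to work and using public transport in March-April, before or early in the restrictions. Asked in the telephone interview, they precede the study's own test result, which limits, though does not remove, recall that depends on infection.

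(b) In sections 2.2 and 5.3.2, say that the mobility-risk objective rests on the cohort: mobility reported at a visit by participants still negative, related to later seroconversion. State which mobility items are repeated at each visit. Report the cross-sectional associations with Q8-Q11, Q15-Q16 and Appendix 2 item 8 as current behaviour, not as risk factors.

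(c) Do not treat Q5-Q7, Q24 or Q29 as strictly preceding infection. The travel and contact items run from February or March up to the interview, Q24 (household) is in the present tense, and Q29 covers the 12 months up to now.

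The cost of (a) is a few seconds in a call of about 10 minutes, plus some recall error. The cost of (b) is a change of wording and a mobility result that comes later and is less precise, because it rests on fewer incident cases.

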## **2. Study objectives**

### **2.1.Primary objective**

**Pilot study:** to evaluate the proportion of people in St. Petersburg, Russia who have had the SARS-CoV-2 infection by means of analyzing the results of the blood serum tests for antiviral antibodies.

**Cohort study:** to evaluate the dynamics of the SARS-CoV-2 infection spread (incidence) by means of analyzing the results of blood serum tests for antiviral antibodies.

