#### **3.2.2. Study exclusion criteria:**

- 3.2.2.1. Refusal to take part in any of the study surveys.
- 3.2.2.2. Impossibility to perform an anti-SARS-CoV-2 antibody test.
- 3.2.2.3. Signs or symptoms of an acute respiratory infection at the moment of a survey or a test, based on the information provided by the participant or on the results of an examination at the investigational site. (The symptoms of an acute respiratory infection may include fever, cough, runny nose, loss of olfaction, marked weakness, dyspnea. A final decision on the presence or absence of the symptoms will be taken on the basis of analysis of observed and medical data).
- 3.2.2.4. Participants younger than 18 years old cannot take part in this study.
- 3.2.2.5. Residence in distant district of the city (Kronshdatsky, Kurortny, Petrodvortsovy, Krasnoselsky, Kolpinsky, Pushkinsky)

Participation in the study is not limited by a single blood draw and anti-SARS-CoV-2 antibody test. The consent to the information transfer maintains for similar repetitive tests and other medical information necessary in the frame of this study.

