## CATI: Study of the spread of COVID-19 in St Petersburg, Russia

Good afternoon! My name is \_\_\_\_\_. The European University at St. Petersburg together with Scandinavia clinics perform a study of coronavirus spread in St. Petersburg residents. It is a very important study which will help to make decisions on the duration of self-isolation, and it gives residents an opportunity of a free-of-charge test to discover if you have already had the infection, as it may be asymptomatic.

Please answer several questions of this survey; it will take about 10 minutes.

a) At the end of this survey, if you are interested in this testing, I will explain in which clinics you can do it and ask your contact information, for the reception contacting you and giving you an appointment at time which suits you.

b) At the end of this survey, if you are interested in this testing, I will explain in which clinics you can do it and ask your contact information, for the reception contacting you and giving you an appointment at time which suits you. In this study, the testing is free-of-charge, and the commuting to the clinic will be also covered: you will receive a personal promocode for a taxi.

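### The printed test offer at Q36 says the antibody test shows current infection, which the interviewer clarification in the same call script denies

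*Protocol*

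**What the plan says.** Appendix 1 of the Protocol is the telephone script. It describes the test in three places.

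- **Opening.** The respondent is told of "a free-of-charge test to discover if you have already had the infection, as it may be asymptomatic".
- **Clarifications for the interviewer, after the opening.** "It shows if you have had a coronavirus infection earlier", and then "It does not show if you are currently infected".
- **Q36, the offer itself.** The respondent is told that "it will show if you have or have not had the infection (or have it now"). This sentence stands before variants a) and b), which differ in the taxi offer and each end by asking for agreement.

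The pilot objective in section 2.1 is to estimate the proportion of people "who have had the SARS-CoV-2 infection by means of analyzing the results of the blood serum tests for antiviral antibodies". That too concerns past infection.

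Two filters come before the offer, one for residence ("If Q2=2, terminate the interview") and one for age ("If Q4(ValueInt<18), terminate the interview"). A second interviewer note, after the offer, refers questions about the test's medical characteristics to the clinic, which calls later.

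**The concern.** The two statements about current infection cannot both be correct, and the one that conflicts with the rest of the Protocol sits in the text to which the respondent says yes or no. The correct statement is in a note headed for the interviewer, and nothing requires it to be read out.

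Two things could follow:

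- **Misread results.** Section 3.4 has results returned to participants. A person told that the test detects present infection could take a negative antibody result as evidence of not being infected now.
- **Selection.** Section 5.2 is concerned that the respondent's own decision to take part may bias the results, and section 1 criticises other surveys for recruiting people more likely to have antibodies. An apparent offer to detect current infection gives people who suspect it a further reason to accept.

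**Working it through.** The Protocol states no figure on this point, so the check is a comparison of texts.

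**Step 1: what the test is said to show.**

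- Section 2.1 (pilot objective): past infection.
- Appendix 1, opening: past infection.
- Appendix 1, first interviewer note: earlier infection, and expressly not current infection.
- Appendix 1, Q36: past infection, or current infection.

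Three places agree or are compatible. Q36 alone adds current infection, and the first interviewer note directly denies that addition.

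**Step 2: whether the respondent is corrected before agreeing.** The opening mentions only past infection but does not rule out current infection. The denial is in the interviewer note. The note after the offer defers questions on the test to the clinic's call. Nothing in the script guarantees a correction before the answer to Q36.

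**Step 3: whether the body of the Protocol covers the gap.** Section 3.4 cautions against reading results as evidence of protection, which is a different matter. Exclusion 3.2.2.3 removes people with "Signs or symptoms of an acute respiratory infection at the moment of a survey or a test". That limits the effect, but it does not reach people without symptoms who suspect infection, for example after a contact. The script asks no question about current symptoms before the offer; Q22 only counts illnesses since February.

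**Step 4: whether the effect on prevalence can be sized.** Let w be the share of tested people who suspect current infection, p1 their seropositivity and p0 that of the rest. Crude prevalence is

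p0 + w × (p1 − p0).

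If the wording raises w by d, and the additional accepters have the same seropositivity p1, crude prevalence changes by

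d × (p1 − p0).

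The Protocol gives none of d, p1 or p0 for these groups. The sign is that of p1 − p0. It is positive if people who suspect infection have more often had it. It is negative if enough of them are tested before antibodies appear, which is also how a falsely reassuring negative result would arise. Neither size nor direction follows from the document.

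**Step 5: the randomised comparison.** The disputed sentence precedes both variants, so as printed it is the same with and without the taxi offer. It may affect who accepts overall. It does not create a difference between the randomised groups.

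**The case against.** The strongest reply is that this is a slip in a call script with safeguards around it. The opening describes the test correctly, exclusion 3.2.2.3 covers people with symptoms, and section 3.1 requires signed consent before the blood test. The information sheet is not available for this review and may say plainly what the test shows. Section 5.3 also plans prevalence estimates corrected for selection on observed and unobserved characteristics. Most of this stands, and it is why the point is minor. It does not remove the contradiction: the respondent agrees at Q36, before signing anything, and on the printed wording.

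Three stronger readings are tempting, and the Protocol does not support them.

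- *Everyone surveyed hears the sentence.* Refusers, non-residents and minors leave earlier. Q36 is also driven by a code with four texts, and all four break off in the available copy before the disputed words, so what is delivered under each code cannot be seen.
- *Prevalence is biased upwards by a calculable amount.* Any such figure would rest entirely on assumed inputs, and the choice of inputs would fix its sign.
- *The encouragement design is undermined.* The wording is common to both variants, and nothing shows that the selection-corrected estimates would be affected.

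**Conclusion.** The point holds as a factual inconsistency in participant-facing text. Q36 contradicts the interviewer clarification in the same script and departs from the past-infection purpose given in the opening and in section 2.1. Respondents who reach the printed offer are misinformed about the test when they decide.

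Both consequences, a misread negative result and added self-selection, are reasonable inferences that the Protocol neither states nor allows to be sized. The conclusion assumes that the printed Q36 wording is what is read out under at least some codes. It does not depend on any bias being present, because an incorrect statement about what a test shows should be corrected even if its effect on the estimates is nil. Severity is minor.

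**What to change.** Delete the parenthetical words about present infection from the Q36 offer, and from any of the four coded texts that contain them. In their place use the script's own clarification, that the test shows earlier infection and does not show current infection, so that the respondent hears it before being asked to agree. Check that the information sheet says the same.

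The cost is a few words in the script and notification of the ethics committee. Acceptance may fall slightly among people looking for a test of current infection. The sample size, the randomised taxi offer and the analysis need no change.
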